8.3. Exploratory Efficacy Endpoint(s) and Analyses

The exploratory efficacy analyses will be based on Efficacy Completers Population. Due to COVID-19 impact, any efficacy data collected outside of the SAP-defined visit window of Month 18 of age visit (older than 570 days of age) will be grouped into “Month 19 of age or older” and included for summary tables unless specified. The hypothesis testing will be based on the data collected up to 18 months of age. Those data will also be included in the corresponding listing.

8.3.1. Proportion of Patients that Achieve Ability to Hold Head Erect Without Support

The ability to hold head erect without support is defined by BSIDv03 Gross Motor Subtest Item #4 and will be based upon the maximum function achieved at any time point up to 18 months of age.

The numbers and percentages of patients who achieve the ability to hold head erect without support by the final visit will be presented by overall, including subgroups, age at the time of treatment (≤ 4 months, > 4 months). The observed proportion achieving the ability to hold head erect without support during the observation period will be compared to zero using a 1-sided Exact Binomial Test, along with the corresponding 97.5% confidence intervals. To make computation of the p-value possible, the value of 0.1% will be used in place of a literal zero.

8.3.2. Proportion of Patients that Achieve Ability to Roll Over

The ability to roll from back to both sides is defined by BSIDv03 Gross Motor Subtest Item #20 and will be based upon the maximum function achieved at any time point up to 18 months of age.

The numbers and percentages of patients who achieve the ability to roll from back to both sides by the final visit will be presented by overall and by subgroups, including subgroups, age at the time of treatment (≤ 4 months, > 4 months). The observed proportion attaining the ability to roll from back to both sides during the observation period will be compared to zero using a 1-sided Exact Binomial Test, along with the corresponding 97.5% confidence intervals. To make computation of the p-value possible, the value of 0.1% will be used in place of a literal zero.

8.3.3. Proportion of Patients that Achieve Functional Independent Sitting for at least 30 seconds

The ability to sit without support is defined by BSIDv03 item #26 and will be based upon the maximum function achieved at any time point up to 18 months of age.

The numbers and percentages of patients who achieve the ability to sit with support will be presented by overall and by subgroups, including age at the time of treatment (≤ 4 months, >4 months). The observed proportion attaining the ability to sit with support during the observation period will be compared to zero using a 1-sided Exact Binomial Test, along with the corresponding 97.5% confidence intervals. To make computation of the p-value possible, the value of 0.1% will be used in place of a literal zero.

8.3.4. Proportion of Patients that Achieve ability to stand with assistance for at least 2 seconds

The ability to stand with assistance for at least 2 seconds is defined by BSIDv03 Gross Motor Subtest Item #33 and will be based upon the maximum function achieved at any time point up to 18 months of age.

The numbers and percentages of patients who achieve the ability to stand with assistance for at least 2 seconds will be presented by overall and by subgroups, including age at the time of treatment (≤ 4 months, >4 months). The observed proportion attaining the ability to stand with assistance for at least 2 seconds during the observation period will be compared to zero using a 1-sided Exact Binomial Test, along with the corresponding 97.5% confidence intervals. To make computation of the p-value possible, the value of 0.1% will be used in place of a literal zero.

8.3.5. Proportion of Patients that Achieve ability to crawl forwards on hands and knees for a distance of at least 5 feet

The ability to crawl forwards on hands and knees for a distance of at least 5 feet is defined by BSIDv03 Gross Motor Subtest Item #34 and will be based upon the maximum function achieved at any time point up to 18 months of age.

The numbers and percentages of patients who ability to crawl forwards on hands and knees for a distance of at least 5 feet during will be presented by overall and by subgroups, including age at the time of treatment (≤ 4 months, >4 months). The observed proportion attaining the ability to crawl forwards on hands and knees for a distance of at least 5 feet during the observation period will be compared to zero using a 1-sided Exact Binomial Test, along with the corresponding 97.5% confidence intervals. To make computation of the p-value possible, the value of 0.1% will be used in place of a literal zero.

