5.4. Clinical Studies

First-in-human trial AVXS-101-CL-101 is a completed 2-year trial which evaluated the efficacy and safety of AVXS-101 in 15 SMA Type 1 patients with 2 copies of *SMN2*. All patients have received a single IV dose of AVXS-101 in 2 cohorts: Cohort 1 (n = 3) received 6.7×10^{13} vg/kg and Cohort 2 (n = 12) received 2.0×10^{14} vg/kg (proposed therapeutic dose). After the End of Trial visit, patients were invited to participate in a long term follow up study conducted under a separate protocol.

- Based on data obtained in Study AVXS 101-CL-101, the following conclusions can be made regarding the efficacy of AVXS 101:
- AVXS 101 administration had a positive effect on survival. Twenty-four months after dosing, all 15 patients were alive and free of permanent ventilation 24 months after dosing and all Cohort 2 patients had survived free of permanent ventilation, a statistically significant difference compared with the natural history rate of 8% reported by Finkel et al 2014 [23].
- Based on independent video reviews, developmental milestones were achieved and maintained over time.
 - In Cohort 2, 11 patients (91.7%) could hold their head erect without support for ≥ 3 seconds and sit with support, 9 patients (75.0%) were able to sit without support for ≥ 30 seconds, and 2 patients each (16.7% each) were able to stand with assistance, stand alone, walk with assistance, and walk alone
- The improvements in Children's Hospital of Philadelphia Infant Test of Neuromuscular Disorders (CHOP INTEND) scores from baseline in both cohorts were sustained over time.
- Nearly all Cohort 2 patients (11/12, 91.7%) achieved a score ≥ 50 on the CHOP INTEND, approximating the range of scores for Type 2 SMA children reported in the Pediatric Neuromuscular Clinical Research Network (PNCR) study [23].
- Other clinically meaningful milestones were maintained 24 months after AVXS-101 infusion:
 - Of the 7 patients in Cohort 2 who did not require non-oral nutrition prior to AVXS-101 dosing, 5 (71.4%) maintained the ability to thrive
 - Eleven Cohort 2 patients (91.7%) were still able to swallow effectively enough to feed orally
 - Seven of 15 patients (46.7%) remained independent of ventilatory support

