4.2. Exploratory Efficacy Endpoints: (see [Section 8](#) for Details)

For the following exploratory efficacy endpoints from achieving the ability to hold head erect to the ability to walk alone, only post-dosing achieved developmental milestones are considered. Milestones observed at baseline will not be counted in the summary table.

1. Proportion of patients that achieve the ability to hold head erect without support as defined by BSIDv03 Gross Motor Subtest Item #4
2. Proportion of patients that achieve the ability to roll over as defined by BSIDv03 Gross Motor Subtest Item #20
3. Proportion of patients that achieve functional independent sitting for at least 30 seconds as defined by BSIDv03 Gross Motor Subtest Item #26
4. Proportion of patients that achieve ability to stand with assistance for at least 2 seconds as defined by BSIDv03 Gross Motor Subtest Item #33

5. Proportion of patients that achieve to crawl forwards on hands and knees for a distance of at least 5 feet as defined by BSIDv03 Gross Motor Subtest Item #34
6. Proportion of patients that achieve to walk with assistance as defined by BSIDv03 Gross Motor Subtest Item #37
7. Proportion of patients that achieve to stand alone for at least 3 seconds as defined by BSIDv03 Gross Motor Subtest Item #40
8. Proportion of patients that achieve to walk at least 3 steps without support as defined by BSIDv03 Gross Motor Subtest Item #42
9. Proportion of patients that achieve the ability to crawl as defined by WHO Motor Developmental Milestones
10. Proportion of patients that achieve the ability to stand with assistance as defined by WHO development milestones
11. Proportion of patients that achieve the ability to stand alone as defined by WHO development milestones
12. Proportion of patients that achieve the ability to walk with assistance as defined by WHO development milestones
13. Proportion of patients that achieve the ability to walk alone as defined by WHO development milestones
- Improvement of raw score from baseline to the maximum using the Bayley Scales of Infant and Toddler Development (Version 3)
14. , Fine and Gross Motor Function Subtests
15. Maximum change from baseline to maximum CHOP-INTEND score
 - Proportion of patients achieving CHOP-INTEND score ≥ 40
 - Proportion of patients achieving CHOP-INTEND score ≥ 50
 - Proportion of patients achieving CHOP-INTEND score ≥ 58

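### SAP 8.3.3 defines the 30-second milestone as sitting without support, but its count and test sentences name sitting with support

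*SAP*

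**What the plan says.** The title of SAP 8.3.3 is "Proportion of Patients that Achieve Functional Independent Sitting for at least 30 seconds". Its first sentence gives the definition: "The ability to sit without support is defined by BSIDv03 item #26".

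The two sentences that specify the analysis then name something else:

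- Count: "The numbers and percentages of patients who achieve the ability to sit with support will be presented by overall and by subgroups".
- Test: "The observed proportion attaining the ability to sit with support during the observation period will be compared to zero". This is a one-sided exact binomial test, in which "the value of 0.1% will be used in place of a literal zero".

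The endpoint list in SAP 4.2, item 3, reads "Proportion of patients that achieve functional independent sitting for at least 30 seconds as defined by BSIDv03 Gross Motor Subtest Item #26". Protocol 11.2.2 describes item #26 as sitting for 30 seconds with no external support from a person or object, although the child may use the arms.

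**The concern.** The count and test sentences are the ones a programmer works from, and in both the named ability differs from the one defined just above. Followed literally, they would put a different and easier ability into the table and the p-value under the heading of independent sitting. The change would tend to favour the product.

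Two features of the SAP weaken the obvious safeguards. SAP 2 says that the SAP supersedes the statistical considerations in the protocol, so the protocol's correct wording does not automatically prevail. The SAP also uses the label functional independent sitting for the 10-second primary milestone (SAP 3.7, 3.11.1 and 8.1.1), whereas protocol 11.2.2 gives that label to item #26. The title of 8.3.3 is therefore a less certain guide than it looks.

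**Working it through.** **1. The wording, side by side**

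| Place | Ability named |
|---|---|
| SAP 8.3.3, title | Functional independent sitting, 30 s |
| SAP 8.3.3, definition | Sitting without support, item #26 |
| SAP 8.3.3, count | Sitting **with** support |
| SAP 8.3.3, test | Sitting **with** support |
| SAP 3.3; SAP 4.2 item 3 | Functional independent sitting, item #26 |
| SAP Appendix 17.1 | Item #26 labelled as sitting without support; no row for supported sitting |
| Protocol 6.3, 11.2.2, 14.1.1.1.3, Appendix 4 | Independent or unsupported sitting, item #26 |

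Only the two analysis sentences of 8.3.3 depart from the rest. The neighbouring sections 8.3.1, 8.3.2, 8.3.4 and 8.3.6 each repeat their own defined ability in the count and test sentences, so this is not a pattern of the template.

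**2. The plan's own figure for this type of test**

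SAP 3.7 states power above 95% with 25 patients for the primary endpoint, against 0.1%, one-sided alpha 0.025, with true response 20% to 50%. SAP 8.3.3 uses the same test and gives no figure of its own.

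- With n = 25, one responder is enough to reject: 1 − 0.999^25 = 0.0247, which is below 0.025.
- Power at 20% is 1 − 0.8^25 = 0.9962; at 50% it is about 1.000. The stated figure is reproduced.
- With n = 30, one responder gives 1 − 0.999^30 = 0.0296, so two are needed. Alpha is then 0.0004 and power at 20% is 98.9%.

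Exploratory analyses use the Efficacy Completers (SAP 8.3), whose final size is not known; 25 and 30 are the planned ITT minimum and the planned enrolment.

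**3. Direction of the error, by illustration**

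Protocol 5.4, Phase 1 Cohort 2 (n = 12):

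- Sitting with support, reported jointly with holding the head erect: 11/12 = 91.7% (exact two-sided 95% CI 61.5% to 99.8%).
- Sitting without support for at least 30 s: "9 patients (75.0%) were able to sit without support", that is 9/12 (42.8% to 94.5%).
- Difference: 11/12 − 9/12 = 2/12 = 16.7 percentage points.

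At those rates, 30 patients would give 30 × 11/12 = 27.5 against 30 × 9/12 = 22.5 responders; 25 patients would give 22.9 against 18.75. Power is about 100% at either rate, so the reported proportion and its interval would change but the decision to reject would not.

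**4. The null value**

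SAP 3.7 bases the near-zero rate on natural history for unsupported sitting and for other milestones, giving rolling over, standing and walking as examples. It gives no untreated rate for supported sitting. The rates below are assumptions. The probability of rejecting 0.1% with no treatment effect is P(X ≥ r) with X binomial(n, q):

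| Assumed untreated rate q | n = 25, r = 1 | n = 30, r = 2 |
|---|---|---|
| 1% | 22% | 3.6% |
| 5% | 72% | 45% |
| 10% | 93% | 82% |

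For example, at n = 25 and q = 5%: 1 − 0.95^25 = 0.72. These figures show only that the p-value for supported sitting would be hard to interpret without a null chosen for that ability.

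**The case against.** The strongest reply is that this is a slip of the pen and would probably do no harm. The title, the definition and the item number all point to unsupported sitting, as does every other description of the endpoint. SAP 6.2.4.3 takes milestone dates from central review of items on the milestone checklist, and supported sitting is not among the milestones listed in Appendix 17.1. A programmer keyed to item #26 would get the right variable. Nearby sections contain other plain slips, such as a missing verb in 8.3.5 and a doubled word in 8.3.7. All of this stands, and it is why drafting error is the likely explanation. It does not make the two sentences correct.

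The Phase 1 comparison is also open to fair criticism. The gap is two patients out of 12, the intervals overlap widely, and the 11/12 is joint with head control. Those outcomes were reported 24 months after dosing, whereas this endpoint closes at 18 months of age. The comparison supports a direction but gives no estimate for this trial.

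A reader might go further and infer that the sponsor chose to analyse an easier milestone, or that the text specifies the opposite of the endpoint. The documents support neither. Nothing outside these two sentences suggests such a choice, and supported sitting is a lower level of the same ability, which unsupported sitters would normally also meet. Nor do the documents rank item #26 as the most important exploratory milestone; protocol 11.3 gives it repeat central review at 18 months, and that is all.

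**Conclusion.** SAP 8.3.3 is internally inconsistent, and its two analysis sentences are wrong as written. The consequence depends on literal programming: the section would then report the wrong variable, tend to overstate the proportion, and test it against a null not justified for that ability. The size of any overstatement in this trial cannot be estimated; the 16.7 points from Phase 1 are an illustration.

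It might also be inferred that the sitting result as a whole is in doubt. It is not. The primary 10-second analysis in SAP 8.1.1 is worded for sitting without support. The 30-second endpoint is exploratory and outside the two-step hierarchy of SAP 8.4. The primary and secondary conclusions and the stated power do not change.

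**What to change.** In both analysis sentences of SAP 8.3.3, replace *sit with support* by *sit without support for at least 30 seconds (BSIDv03 Gross Motor item #26)*. Check that the table shell for this endpoint draws on item #26. The cost is two phrases and one check; no sample-size or power figure, test or data collection changes.

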8.3.6. Proportion of Patients that Achieve ability to pull to stand

The ability to pull to stand is defined by BSIDv03 Gross Motor Subtest Item #35 and will be based upon the maximum function achieved at any time point up to 18 months of age.

The numbers and percentages of patients who achieve the ability to pull to stand will be presented by overall and by subgroups, including age at the time of treatment (≤ 4 months, >4 months). The observed proportion attaining the ability to pull to stand during the observation period will be compared to zero using a 1-sided Exact Binomial Test, along with the corresponding 97.5% confidence intervals. To make computation of the p-value possible, the value of 0.1% will be used in place of a literal zero.

8.3.7. Proportion of Patients that Achieve ability to walk with assistance

The ability ability to walk with assistance is defined by BSIDv03 Gross Motor Subtest Item #37 and will be based upon the maximum function achieved at any time point up to 18 months of age.

The numbers and percentages of patients who achieve the ability to walk with assistance will be presented by overall and by subgroups, including age at the time of treatment (≤ 4 months, >4 months). The observed proportion attaining the ability to walk with assistance during the observation period will be compared to zero using a 1-sided Exact Binomial Test, along with the corresponding 97.5% confidence intervals. To make computation of the p-value possible, the value of 0.1% will be used in place of a literal zero.

8.3.8. Proportion of Patients that Achieve ability to stand alone for at least 3 seconds

The ability ability to stand alone for at least 3 seconds is defined by BSIDv03 Gross Motor Subtest Item #40 and will be based upon the maximum function achieved at any time point up to 18 months of age.

The numbers and percentages of patients who achieve the ability to stand alone for at least 3 seconds will be presented by overall and by subgroups, including age at the time of treatment (≤ 4 months, >4 months). The observed proportion attaining the ability to stand alone for at least 3 seconds during the observation period will be compared to zero using a 1-sided Exact Binomial Test, along with the corresponding 97.5% confidence intervals. To make computation of the p-value possible, the value of 0.1% will be used in place of a literal zero.

8.3.9. Proportion of Patients that Achieve ability to walk at least 3 steps without support

The ability ability to walk at least 3 steps without support is defined by BSIDv03 Gross Motor Subtest Item #42 and will be based upon the maximum function achieved at any time point up to 18 months of age.

The numbers and percentages of patients who achieve the ability to walk at least 3 steps without support will be presented by overall and by subgroups, including age at the time of treatment (≤ 4 months, >4 months). The observed proportion attaining the ability to walk at least 3 steps without support during the observation period will be compared to zero using a 1-sided Exact Binomial Test, along with the corresponding 97.5% confidence intervals. To make computation of the p-value possible, the value of 0.1% will be used in place of a literal zero.

8.3.10. Proportion of Patients That Achieve Ability to Crawl

The ability to crawl is defined by WHO development milestones and will be based upon the maximum function achieved at any time point up to 18 months of age.

The numbers and percentages of patients who achieve the ability to crawl will be presented by overall and by subgroups, including subgroups, age at the time of treatment (≤ 4 months, >4 months). The observed proportion attaining the ability to crawl during the observation period will be compared to zero using a 1-sided Exact Binomial Test, along with the corresponding 97.5% confidence intervals. To make computation of the p-value possible, the value of 0.1% will be used in place of a literal zero.

8.3.11. Proportion of Patients that Achieve the Ability to Stand with Assistance

The ability to stand with assistance is defined by WHO development milestones and will be based upon the maximum function achieved at any time point up to 18 months of age.

The numbers and percentages of patients who achieve the ability to stand with assistance will be presented by overall and by subgroups, including subgroups, age at the time of treatment (≤ 4 months, >4 months). The observed proportion attaining the ability to stand with assistance during the observation period will be compared to zero using a 1-sided Exact Binomial Test, along with the corresponding 97.5% confidence intervals. To make computation of the p-value possible, the value of 0.1% will be used in place of a literal zero.

8.3.12. Proportion of Patients that Achieve Ability to Stand Alone

The ability to stand alone is defined by WHO development milestones and will be based upon the maximum function achieved at any time point up to 18 months of age.

The numbers and percentages of patients who achieve ability to stand alone by the final visit will be presented by overall and by subgroups, including subgroups, age at the time of treatment (≤ 4 months, >4 months). The observed proportion achieving ability to stand alone during the observation period will be compared to zero using a 1-sided Exact Binomial Test, along with the corresponding 97.5% confidence intervals. To make computation of the p-value possible, the value of 0.1% will be used in place of a literal zero.

8.3.13. Proportion of Patients that Achieve Ability to Walk with Assistance

The ability to walk with assistance is defined by WHO development milestones and will be based upon the maximum function achieved at any time point up to 18 months of age.

The numbers and percentages of patients who achieve ability to walk with assistance by the final visit will be presented by overall and by subgroups, including subgroups, age at the time of treatment (≤ 4 months, >4 months). The observed proportion achieving ability to walk with assistance during the observation period will be compared to zero using a 1-sided Exact Binomial Test, along with the corresponding 97.5% confidence intervals. To make computation of the p-value possible, the value of 0.1% will be used in place of a literal zero.

8.3.14. Proportion of Patients that Achieve Ability to Walk Alone

The ability to walk alone is defined by WHO development milestones and will be based upon the maximum function achieved at any time point up to 18 months of age.

The numbers and percentages of patients who achieve ability to walk alone by the final visit will be presented by overall and by subgroups, including subgroups, age at the time of treatment (≤ 4 months, >4 months). The observed proportion achieving ability to walk alone during the observation period will be compared to zero using a 1-sided Exact Binomial Test, along with the corresponding 97.5% confidence intervals. To make computation of the p-value possible, the value of 0.1% will be used in place of a literal zero.

8.3.15. Improvement of Raw Score and Scaled Score using Bayley Scales of Infant and Toddler Development (Version 3), Fine and Gross Motor Function Subtests

Descriptive statistics for change from baseline in Fine and Gross motor function raw and scaled scores will be presented at each Study Day based visit, including mean, standard deviation, median, minimum, and maximum values.

Descriptive statistics for change from baseline in Fine and Gross motor function raw and scaled scores will also be presented at each Age Based visit, including mean, standard deviation, median, minimum, and maximum values.

The change from baseline of Bayley raw score to maximum score at any visit will be presented at by overall. An ANCOVA model with subgroup variable, as the factor and baseline Bayley score as a covariate, will be used to evaluate the comparability of the maximum change of Bayley score between subgroups.

The change from baseline will be analyzed by using mixed model with repeated measurement (MMRM). The model will include the change from baseline as the dependent variable, and fixed effects of subgroup, visit, and a covariate of baseline, age at baseline, and interactions of subgroup*visit, baseline*visit. A Toeplitz covariance structure will be assumed initially to model the within-patient errors; however, if the covariance structure results in non-convergence, the structure of compound symmetry will be used. The mean change from baseline (%), least squares (LS) means, differences between LS means, a 95% 2-sided CLs for each difference and the p-values from model effects will be reported for each scheduled visit through Month 18.

